FitLink: Improving Weight Loss Maintenance by Using Digital Data to Provide Support and Accountability

NCT03337139

Document date: October 30, 2020

Study Protocol and Statistical Analysis Plan

Setting and Population

This was a single-site, pilot randomized controlled clinical trial. Participants were recruited from the community from October 2017 to March 2018. Follow-up assessments were completed in May 2019. Inclusion criteria included age 18 to 70 years; BMI 25-45 kg/m²; regular access to a smartphone and internet connection; ability to begin a program of physical activity; and completion of all enrollment procedures. Participants were excluded if they had a medical condition or psychiatric condition (e.g., active substance abuse, eating disorder) that could pose a risk or limit ability to comply with program recommendations. Participants were also excluded if they were pregnant or planning to become pregnant or move out of the area during the data collection period, were using a pacemaker, had a history of bariatric surgery, had recently begun or changed the dose of a medication that could cause a significant change in weight, or if they had a weight loss of $\geq 10\%$ in the previous 3 months. The most common reasons for exclusion were out-of-range BMI (n = 34) and lack of availability at group meeting times (n = 30). All participants provided informed consent, and all study procedures were approved by the Institutional Review Board at Drexel University, where the study was conducted.

Phase I: Uniform, Initial Weight Loss Treatment

All participants received identical treatment during Phase I, the initial, face-to-face phase of treatment. Participants attended 12, weekly behavioral weight loss group sessions. The treatment protocol was adapted from Look AHEAD and the Diabetes Prevention Program (14, 15). Treatment included problem solving skills, strategies for stimulus control, goal setting, and social support skills. Participants were given prescriptions for reducing calorie intake and were told to gradually increase their moderate-to-vigorous physical activity (MVPA) to 250 bouted minutes per week (i.e., a minimum of 10 minutes of exercise at a time).

All participants were provided with three self-monitoring tools: a Yunmai Smart Scale for measuring body weight, a Fitbit Flex for monitoring physical activity, and the Fitbit app for recording food intake and viewing data from all three devices. Participants were told to weight themselves weekly in weeks 1-10 and daily thereafter; to wear the physical activity sensor daily, paying particular attention to "active minutes" when reviewing device data; and to record food intake daily. During Phase I, device data were not available to counselors. Participants were instructed not to share device data with friends, family, or other participants at any point in the program.

Phase II: Remote Maintenance Treatment

At the conclusion of Phase I, participants were randomly assigned (matching for initial weight loss) to one of two treatments for Phase II (weeks 13-52): standard lifestyle modification (LM) or lifestyle modification plus device data sharing (LM+SHARE). Phase II treatment was delivered remotely. There were no further group meetings; participants received monthly, individual, 15-minute phone calls and weekly, one-way text messages. Participants in both conditions were instructed to continue using digital devices daily to self-monitor weight, physical activity, and food intake.

In LM+SHARE, counselors had access to a secure online portal that uploaded data from participants' self-monitoring devices. Counselors were instructed to attend to changes in weight, adherence to dietary intake and physical activity goals, and self-monitoring frequency when viewing data. In phone calls and text messages with participants, counselors used their data observations to cultivate a sense of supportive accountability, conveying to participants that they were regularly monitoring adherence to program goals in order to sustain participant success. Counselors set goals with participants in monthly phone calls, subsequently viewed data relevant to the goals to determine if they were being met, and in the text messages and phone calls that followed provided praise to reinforce positive behaviors or expressed concern if adherence was poor. For example, a text message might say: "I'm so impressed that you started recording your food intake again! I saw you recorded for 5 days this week. Reflect on how you accomplished that, and how it was helpful, so that you can carry this success forward. Keep up this fantastic work!" As another example, in a phone call a counselor might say: "You set a goal last month of 5 bouts of exercise per week, and I see that you only averaged 2 per week. Tell me more about what happened." Counselors also used phone calls and text messages to review core behavioral skills or strategies and encourage their use.

In the LM condition, counselors did not have access to device data. Counselors used participant self-report in monthly phone calls (prompted by questions such as, "How successful have you been in meeting your physical activity goals since our last call?") to assess progress and adherence. As in LM+SHARE, LM counselors reviewed one or more core behavioral skills or strategies in each phone call. All participants in the LM condition received standardized, weekly text messages that highlighted a core behavioral skill or strategy; messages in this condition were not personalized.

The seven counselors who provided treatment had degrees in psychology or a related field (1 = PhD, 4 = MA/MS, 2 = BA/BS). Counselors had previous training in behavioral weight loss and also completed a training workshop and weekly supervision for this study. All counselors provided both forms of treatment.

Measures

Assessments were completed at weeks 0 (baseline), 13 (i.e., baseline of Phase II treatment), week 26, and week 52 (end of treatment).

Demographics. Age, gender, education, race, and ethnicity were self-reported at baseline.
Height and weight. At each assessment, research staff weighed participants using a Tanita
model WB-3000 digital scale. Participants were weighed in light street clothes without shoes.
Height was measured at baseline using a stadiometer. Measurements were taken twice and
averaged.

Physical Activity. Participants wore ActiGraph GT3X tri-axial, solid state accelerometers to measure MVPA at weeks 13 and 52. (To minimize "device burden," given that participants were asked upon enrollment to begin using three other self-monitoring devices, Actigraph measurements were not done at week 0.) Participants were told to wear the accelerometer for seven consecutive days during all waking hours, and data were considered valid when available for a minimum of four days for at least 10 hours per day. ActiLife software was used to calculate MVPA using established cut-points (16). Consistent with the intervention focus on bouted exercise, MVPA totals included only episodes of MVPA detected by the accelerometer to be \geq 10 minutes.

Self-monitoring engagement. Device data were collected on a secure online portal, which allowed for calculation of the percent of days during which weight was recorded on the Yunmai Smart Scale; \geq five foods were logged in the Fitbit app; and the Fitbit counted \geq 500 steps.

Treatment engagement. Engagement with treatment phone calls was calculated as the number of calls the participant completed during Phase II, out of 8 possible calls. The number of text messages sent by the counselor also was calculated.

Treatment satisfaction. Treatment satisfaction was measured using the Treatment Acceptability Questionnaire (17), with some items modified to reflect specific treatment components of the current study. This measure has good internal consistency and concurrent validity.

Perceived accountability. The "Perceptions of Accountability" subscale of the Supportive Accountability Scale (18) was administered to measure the extent to which the participants feel accountable to others to achieve their weight control goals. Reliability and validity for this scale has been established (18).

Data Analysis

Retention was compared between the two conditions using Fisher's exact test. Permutation test was conducted to examine the difference between conditions in the number of phone calls and text messages (which could vary if a participant requested that contact be discontinued or temporarily suspended) and treatment acceptability ratings. Permutation test, a type of nonparametric test that uses sampling without replacement to test hypotheses, was chosen due to the violation of t-test assumptions in the data set (19). We conducted permutation based ANCOVA to compare self-monitoring engagement in Phase II between conditions controlling for Phase I self-monitoring engagement. This analytic method was implemented in the "permuco" package in R and has been shown to be robust to data with non-normal distribution (20). ANCOVA was used to test the difference in weight change between conditions, controlling for Phase I weight loss. Change in bouted MVPA during Phase II was compared between LM and LM+SHARE controlling for Fitbit-measured changes in Phase I MVPA using permutation based ANCOVA. One outlier for bouted MVPA at 13 weeks in the LM condition was removed from the analyses (MVPA was more than 3 SDs above others). Repeated measures ANCOVA was used to compare perceived accountability controlling for Phase I change. Analyses examined whether the effect of condition on weight loss during Phase II was mediated by change in monthly adherence to self-monitoring during the first 6 months of Phase II, or change in perceived accountability from weeks 13 to 26. If weight and MVPA outcome data were missing, the most recent data from the participant's digital scale or Fitbit, respectively, were used for imputation; if those data were not available, baseline data were carried forward. Strong associations were found between weight measured in clinic and via home digital scale (r= .995, p< .001 at 52 weeks), and between Actigraph and Fitbit measurements of MVPA (r = .60, p < .001 at 52 weeks), validating this missing data approach. The study was designed as a pilot randomized trial, with a focus on having a large enough sample for estimates of feasibility, acceptability, and effect sizes to be reliable. Data were analyzed in SPSS version 25 and R version 4.0.0.

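### Allocation was matched on initial weight loss, but the permutation tests of calls, texts and acceptability name no covariate and no restriction to matched sets; they are conservative if weight loss predicts those outcomes

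*Combined protocol and SAP*

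**What the plan says.** Under Phase II: Remote Maintenance Treatment, "participants were randomly assigned (matching for initial weight loss) to one of two treatments". The text does not say whether this was done by pairs, strata or another method.

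The Data Analysis section then treats the outcomes differently:

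- **Weight change:** "ANCOVA was used to test the difference in weight change between conditions, controlling for Phase I weight loss". The matching variable is in the model.
- **Calls, texts and acceptability:** "Permutation test was conducted to examine the difference between conditions in the number of phone calls and text messages"; the same sentence continues "which could vary if a participant requested that contact be discontinued or temporarily suspended) and treatment acceptability ratings". No covariate is named. The permutation scheme is described only in general terms, with nothing on whether shuffles stay within matched sets.
- **Self-monitoring:** "permutation based ANCOVA to compare self-monitoring engagement in Phase II between conditions controlling for Phase I self-monitoring engagement".
- **MVPA:** compared "controlling for Fitbit-measured changes in Phase I MVPA using permutation based ANCOVA".
- **Perceived accountability:** a repeated measures ANCOVA adjusted for Phase I change. The text does not say change in what; the natural reading is change in accountability.
- **Retention:** Fisher's exact test, unadjusted.

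The Measures section defines call engagement as the "number of calls the participant completed during Phase II, out of 8 possible calls". The Data Analysis section describes the study as a pilot "with a focus on having a large enough sample for estimates of feasibility, acceptability, and effect sizes to be reliable".

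**The concern.** A permutation test holds its nominal level when its shuffles mirror the way treatment was allocated. Matching rules out allocations in which the arms differ much on initial weight loss. Unrestricted shuffling puts those allocations back into the reference distribution. If weight loss predicts the outcome, they are the ones that produce large chance differences. The reference distribution is then wider than the true null distribution, and p-values are too large on average.

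Calls and acceptability bear on the feasibility and acceptability that the pilot focuses on. A test that is too conservative could let a real difference between the arms pass as comparability. Any standard error or interval built on the unadjusted variance would also be too wide.

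**Working it through.** **Inputs.** The documents give the matching and the tests, but no sample size, significance level, power target or correlation, so there is no planned figure to reproduce. Assumed here: two-sided 5%; r (correlation of the outcome with Phase I weight loss) from 0 to 0.5; 20 or 40 per arm; close matching; unrestricted permutation; an effect that gives the adjusted test 80% power, i.e. 1.96 + 0.84 = 2.80 standard errors.

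**Step 1: type I error.** Close matching multiplies the true variance of the arm difference by (1 − r²). The unrestricted test still uses the full variance. In true standard errors its critical value is therefore 1.96/√(1 − r²), and its size is 2Φ(−1.96/√(1 − r²)).

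**Step 2: power of the unadjusted test under matching.** Φ(2.80 − 1.96/√(1 − r²)).

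**Step 3: power of the same unadjusted test under simple randomisation.** The estimate now has the full variance, so power is Φ(2.80·√(1 − r²) − 1.96). Size stays at 5%.

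| r | √(1 − r²) | critical value | type I, matched | power, matched | power, simple randomisation |
|---|---|---|---|---|---|
| 0 | 1.000 | 1.960 | 5.0% | 80.0% | 80.0% |
| 0.2 | 0.980 | 2.000 | 4.5% | 78.9% | 78.4% |
| 0.3 | 0.954 | 2.055 | 4.0% | 77.2% | 76.2% |
| 0.5 | 0.866 | 2.263 | 2.4% | 70.5% | 67.9% |

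The gap to the adjusted test's 80% is about 1, 3 and 10 points under matching, and about 2, 4 and 12 points under simple randomisation. So the power gap comes from leaving out a prognostic covariate, and matching makes it slightly smaller. Only the type I error below 5% is specific to ignoring the matching.

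**Step 4: simulated type I error.** With a normal outcome, 80 participants and 499 permutations:

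- Pair matching, unadjusted: 4.7%, 4.1% and 2.5% at r = 0, 0.3 and 0.5.
- Balance within four strata, unadjusted: 4.8%, 4.2% and 3.3%.
- Simple randomisation, unadjusted: 4.6% to 5.4% for r from 0 to 0.7.
- Pair matching, adjusted for weight loss: 4.9% to 5.5% for r from 0 to 0.7.

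**Step 5: outcomes shaped like those in the plan.** These runs used about 30,000 trials per setting, with assumed distributions.

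- *Acceptability-like rating* (capped at 7, mean 5.7), 80 participants, pairs. Unadjusted against adjusted power is .795 and .796 at r = 0, .786 and .797 at 0.2, .769 and .797 at 0.3, and .700 and .794 at 0.5.
- *Calls* (0 to 8, mean 6.5, 36% at 8), 80 participants, pairs. The figures are .779 and .802, .767 and .802, .752 and .800, and .663 and .785. The 2.3-point gap at r = 0 comes from ties, not from weight loss. Taking it off leaves 3.5 − 2.3 = 1.2, 4.8 − 2.3 = 2.5 and 12.2 − 2.3 = 9.9 points.

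Text counts were not simulated.

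**Step 6: models with their own Phase I covariate.** Let a and b be that covariate's correlations with the outcome and with weight loss. The nominal variance is 1 − a², the true variance 1 − a² − (r − ab)², and the variance with weight loss added 1 − a² − (r − ab)²/(1 − b²). With a = 0.5 to 0.6 and b = 0.2 to 0.4 (assumed), the power loss is 0 to 0.4 points at r = 0.2, 0.2 to 1.7 at 0.3, and 4.3 to 8.9 at 0.5. It is zero when r = ab.

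**The case against.** The strongest case against the point is that it stacks conditions the documents do not establish. The permutation must ignore the matching, and the Data Analysis section is silent on that. The matching must be close, and no method is given. And r must be about 0.3 or more, although nothing in the documents links Phase I weight loss to calls, texts or acceptability. All of this stands: it makes the point conditional and leaves its size unknown. It does not remove the point, because unrestricted shuffling is the natural reading and the direction of the effect is certain when the conditions hold.

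Some stronger readings are tempting but not supported:

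- *Matching adds 1, 3 or 10 points of power loss.* It does not. The same unadjusted test has slightly lower power under simple randomisation.
- *The results are biased or carry excess false positives.* Neither follows; the error runs the other way.
- *The pilot's estimates are less reliable.* Under close matching they are not. For the rating with 40 per arm and r = 0.5, the simulated SD of the estimate was .174 with or without adjustment under pairs. Under a coarser median split it was .183 unadjusted against .174. The main harm is to p-values and to any reported standard errors or intervals, and the plan mentions no interval for these outcomes.
- *The whole analysis ignores the design.* Weight change is already adjusted for the matching variable. Self-monitoring, MVPA and accountability carry a Phase I covariate, and the computed loss there is near nil for r up to 0.3.

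Texts are the weakest case. Messages were weekly and one-way, and the only stated source of variation is a participant asking for contact to stop or pause.

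**Conclusion.** The point holds as a minor one. The allocation is matched on initial weight loss, and the tests of calls, texts and acceptability, as written, take no account of it. If shuffling is unrestricted, matching is close and the level is two-sided 5%, actual type I error is about 4.5%, 4.0% and 2.4% at r = 0.2, 0.3 and 0.5. Relative to an adjusted test with 80% power, about 1, 3 and 10 points of power are forgone; this is the usual price of omitting a prognostic covariate. At r of 0.2 or below the effect is negligible, and at r = 0 there is none. Which case applies here cannot be told from the documents. If the permutation did respect the matching, the type I error point largely falls away.

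**What to change.** State how the matching was done and whether the permutations respected it. Then, as a post hoc sensitivity analysis shown beside the original results, do one of the following:

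- compare calls and acceptability (and texts, for consistency) by the permutation-based ANCOVA already in the plan, with Phase I weight loss as covariate; or
- permute within the matched sets, if these were recorded.

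For calls the first option is preferable. In simulation with a 0 to 8 outcome and pair matching, covariate adjustment gave a type I error of 4.6% to 5.4%, while within-pair permutation stayed at 3.6% to 4.3% because of ties.

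Adding weight loss to the self-monitoring, MVPA and accountability models is optional. The retention test need not change.

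The cost is one degree of freedom per model, using weights already measured at weeks 0 and 13. If weight loss turns out not to predict the outcome, little is lost: at r = 0, adjustment changed simulated power for the rating by −0.5 to +0.1 points. Follow-up ended in May 2019 and the Data Analysis section already reports week-52 correlations, so the added analyses cannot replace the originals.

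### The MVPA model adjusts for Fitbit-measured Phase I change but not for week-13 ActiGraph MVPA, the Phase II baseline already collected

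*Combined protocol and SAP*

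**What the plan says.** The MVPA analysis is a permutation-based ANCOVA described in one sentence of Data Analysis: "Change in bouted MVPA during Phase II was compared between LM and LM+SHARE controlling for Fitbit-measured changes in Phase I MVPA". No other covariate is named.

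Under Measures, the assessment schedule labels week "13 (i.e., baseline of Phase II treatment"). The Physical Activity paragraph says participants wore "accelerometers to measure MVPA at weeks 13 and 52", and that, to limit device burden, "Actigraph measurements were not done at week 0".

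Under Phase II: Remote Maintenance Treatment, "participants were randomly assigned (matching for initial weight loss) to one of two treatments for Phase II". MVPA was not a matching factor.

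Three further statements in Data Analysis bear on this model:

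- **Missing MVPA.** The latest data from the digital scale "or Fitbit, respectively, were used for imputation; if those data were not available, baseline data were carried forward".
- **Agreement between devices.** The correlation is given as "between Actigraph and Fitbit measurements of MVPA (r = .60, p < .001 at 52 weeks").
- **Outlier.** "One outlier for bouted MVPA at 13 weeks in the LM condition was removed from the analyses", because the value lay more than 3 SDs above the others.

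**The concern.** A change score subtracts the week-13 value with its coefficient fixed at 1. If the regression of week-52 on week-13 MVPA has a slope below 1, as it must with equal SDs and imperfect correlation, the change score over-corrects. A chance week-13 difference between the arms then reappears, with opposite sign, in the contrast. Estimating the coefficient by entering week-13 MVPA as a covariate removes this.

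The lack of a week-0 ActiGraph reading explains why Phase I change has to come from the Fitbit. It does not prevent use of the week-13 ActiGraph reading. Fitbit Phase I change is a different quantity from a different device, and a weak substitute for the week-13 level. Matching on initial weight loss does not balance MVPA directly.

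What is at stake is precision. The carried-over imbalance and the wider standard error are two views of the same loss and should not be counted twice. Precision matters here because the pilot's stated aims include reliable effect sizes.

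**Working it through.** The plan states no sample size, power or precision figure for MVPA, so there is nothing of its own to reproduce. The check compares the residual variance of the planned model with that of the same model plus week-13 ActiGraph MVPA.

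**Inputs**

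- From the documents: Fitbit-ActiGraph correlation .60, stated for week 52 and assumed to hold in Phase I.
- Assumed: ActiGraph SD 1 at week 13, s at week 52 and s0 at week 0; a common ActiGraph correlation ρ between time points, .4 to .8; Phase II change taken as the simple difference week 52 minus week 13.
- Fitbit = SD × (.6 × standardised ActiGraph + .8 × error), with error correlation ρe over time.

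**Formulas**

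Let X be Fitbit Phase I change.

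- Var(X) = .36(1 + s0² − 2ρs0) + .64(1 + s0² − 2ρe·s0)
- Planned model: Var(change) − Cov(change, X)² / Var(X)
- Fuller model: residual variance of week 52 given week 13 and X

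With s0 = 1 and ρe = ρ these reduce to:

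- planned = 1 + s² − 2ρs − .18(1 − ρ)
- fuller = s²[1 − ρ² / (1 − .18(1 − ρ))]

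**Worked case, s = 1, ρ = .6**

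- planned = 2 − 1.2 − .072 = .728
- fuller = 1 − .36/.928 = .612
- ratio = .728/.612 = 1.19

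**Ratio planned/fuller (ρe = ρ)**

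| Scenario | ρ=.4 | .5 | .6 | .7 | .8 |
|---|---|---|---|---|---|
| Equal SDs | 1.33 | 1.26 | 1.19 | 1.13 | 1.08 |
| Week-52 SD 1.2 | 1.16 | 1.10 | 1.05 | 1.02 | 1.00 |
| Week-52 SD 0.8 | 1.70 | 1.62 | 1.55 | 1.51 | 1.51 |
| Week-0 SD 0.4 | 1.25 | 1.19 | 1.13 | 1.08 | 1.05 |

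For equal SDs the standard-error ratio is √1.08 = 1.04 to √1.33 = 1.15. Setting ρe = .8 changes the equal-SD range to 1.08-1.26; first-order autoregressive correlations give 1.11-1.38.

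**Why the Fitbit term does not stand in for the baseline.** Its correlation with week-13 ActiGraph MVPA is .6(1 − ρs0)/√Var(X). With equal SDs and ρe = ρ this is .33 at ρ = .4 and .19 at ρ = .8. It is about .55 if the week-0 SD is 0.4.

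**Imputation.** This was simulated with 400,000 records, ρ = .4, .6 and .8, and 10-30% of week-52 values missing completely at random. All missing values were replaced either by Fitbit (taken to have the ActiGraph mean and SD) or by week 13 carried forward. Ratios were 1.05-1.38 (equal SDs), 1.00-1.20 (week-52 SD 1.2), 1.29-1.76 (week-52 SD 0.8) and 1.03-1.33 (week-0 SD 0.4). A level difference between devices, missing week-13 values and outcome-related missingness were not modelled.

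**A chance imbalance of 0.2 SD at week 13, equal SDs**

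- Carried into the planned contrast: 0.2(1 − ρ)[1 − .36(1 − ρ)/Var(X)] = 0.2(1 − ρ)(.82), which is .098 at ρ = .4 and .033 at ρ = .8.
- Planned standard error at an assumed 40 per arm: √(1.092 × 2/40) = .234 and √(.364 × 2/40) = .135.
- The shift is therefore .42 to .24 of one standard error. Across week-52 SDs of 1.2 to 0.8 it is .01 to .54.

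**Removed LM participant, equal SDs.** For a value k SDs out among n per arm, the expected shift from removal is (k/n)(1 − ρ)(.82). With k = 3 this is .037-.012 SD at n = 40 and .049-.016 SD at n = 30, or .09-.18 of one standard error. Because the value was more than 3 SDs out, k = 3 is a floor.

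**Cost of the extra covariate.** (N − 3)/(N − 4) = 57/56 = 1.018 at an assumed N of 60 and 77/76 = 1.013 at N = 80.

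**The case against.** The strongest reply is that nothing here is wrong. ANCOVA on change with a pre-randomisation covariate is valid, and adjusting for Phase I change matches the plan's models for weight and perceived accountability. That stands: this is a less efficient choice, not an error.

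Second, the size of the gain is not established. Every input except r = .60 is assumed, and the range includes no gain. With a week-52 SD about 1.2 times week 13 and ρ of .7 or more, the ratio is 1.00-1.02, which the degree of freedom uses up. The largest ratios need a week-52 SD of 0.8, which nothing in the documents supports. No actual imbalance is shown. All of this stands. However, in no scenario was the planned model more precise before that 1-2% cost.

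Third, the document is dated October 2020, follow-up ended in May 2019, and the analyses are described as done. A covariate added now is post hoc and must be labelled so. That affects how the result is presented, not whether it is informative.

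Fourth, some week-13 recordings may fail the wear-time rule. True, but a missing week-13 value affects the planned change score equally.

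Fifth, the outlier removal is fully disclosed and is a separate, smaller matter. Fair. If that participant is put back, the expected effect is near zero with week 13 as a covariate only if the linear relation holds that far out, since the point would have high leverage.

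**Conclusion.** The point holds. Week-13 ActiGraph MVPA is the Phase II baseline, it was collected, and it is not named as a covariate. The planned contrast is unbiased over randomisation but usually less precise than the same model with that value added.

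The central estimate, with equal SDs and ρ of .4 to .8, is a standard error 4-15% larger than necessary; the overall variance ratio is about 1.0 to 1.8. These figures rest on assumed SDs, correlations and missingness, on reading change as a simple difference, and on the week-52 device correlation applying in Phase I. Confidence is medium. The change should be made because it is nearly free and serves the pilot's aim of reliable effect sizes. It does not invalidate the planned result.

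**What to change.** Add week-13 ActiGraph bouted MVPA as a covariate in the permutation ANCOVA and keep Fitbit Phase I change. The outcome can remain change: once its own baseline is in the model, the condition effect is identical to that for the week-52 level. As the outcomes are already known, report this alongside the planned result and label it as added afterwards.

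Report the MVPA result both with and without the removed LM participant. Which version is the main one is for the sponsor to decide.

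The cost is one covariate and one extra run of one model, on data in hand, with no participant burden. It uses one degree of freedom, about 1-2% of variance at an assumed N of 60-80, and brings no net gain if the week-52 SD is about 1.2 times week 13 and ρ is .7 or more.

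### Adjusting perceived accountability for Phase I change alone is never more precise than adjusting for the week-13 and week-0 scores separately; the size of the loss depends on a model the plan leaves unstated

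*Combined protocol and SAP*

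**What the plan says.** The model for this outcome is given in one sentence of the Data Analysis section: "Repeated measures ANCOVA was used to compare perceived accountability controlling for Phase I change". No other covariate is named. The section does not say which weeks are the repeated levels, or whether the tested term is the main effect of condition or condition by time.

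The Measures section gives the general schedule: "Assessments were completed at weeks 0 (baseline), 13 (i.e., baseline of Phase II treatment), week 26, and week 52 (end of treatment"). It lists no administration weeks for the accountability subscale, saying only that it "was administered to measure the extent to which the participants feel accountable to others to achieve their weight control goals". A week-0 and a week-13 score are implied by the use of Phase I change, and a week-26 score by the mediation analysis, which names as one candidate mediator "or change in perceived accountability from weeks 13 to 26".

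Under Phase II: Remote Maintenance Treatment, "participants were randomly assigned (matching for initial weight loss) to one of two treatments for Phase II (weeks 13-52"). The week-13 accountability score was therefore not a matching factor. Elsewhere in Data Analysis, self-monitoring in Phase II is compared "controlling for Phase I self-monitoring engagement", that is, adjusting for an earlier level, whereas weight and activity are analysed as changes with a Phase I change as covariate.

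**The concern.** Week 13 is the baseline for the randomised phase, and both it and the week-0 score must be in the data set. A difference score uses them only in one fixed combination: whatever weight week 13 receives, week 0 receives the same weight with the opposite sign. Where each score predicts later accountability in its own right, that combination can discard much or all of the information.

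Accountability is the mechanism through which sharing device data is meant to work, and it is a tested mediator. The plan presents the trial as a pilot whose sample should give reliable effect-size estimates. An avoidably noisy accountability contrast works against that aim, and a contrast whose levels and tested term are unstated is hard to interpret.

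**Working it through.** **Inputs from the document.** The covariate is Phase I change (Data Analysis), read here as the week-13 minus the week-0 accountability score. Visits are weeks 0, 13, 26 and 52 (Measures); week 52 for this scale is inferred from the general schedule. The document gives no SD, correlation or sample size for this outcome, so there is no plan figure to reproduce.

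**Assumptions.** Unit SD at every visit; between-visit correlation ρ = 0.6, with a range of 0.3 to 0.8; either equal correlation or first-order autoregressive by visit; arm effect d equal at weeks 26 and 52 and zero at week 13.

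**Step 1: general result.** Let P = (Y26 + Y52)/2. Scale each candidate analysis so that it estimates d. Its residual variance is then Var(P − b13·Y13 − b0·Y0), and the readings differ only in a constraint on the coefficients:
- Outcomes weeks 26 and 52, covariate Y13 − Y0: P − b(Y13 − Y0), so b13 + b0 = 0.
- Change from week 13, or condition by time: P − Y13 − b(Y13 − Y0), so b13 + b0 = 1.
- Main effect over weeks 13, 26 and 52: the mean is (2P + Y13)/3 and the effect is (0 + d + d)/3 = 2d/3. Multiplying by 3/2 gives P + Y13/2 − b(Y13 − Y0), so b13 + b0 = −1/2.
- Both scores entered separately: no constraint.

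The unconstrained minimum cannot exceed a constrained one. The price is one more estimated coefficient.

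**Step 2: equal correlation, ρ = 0.6.**
- Var(P) = (1 + 0.6)/2 = 0.80, and Var(Y13 − Y0) = 2(1 − 0.6) = 0.80.
- Weeks 26/52 with Phase I change: the covariance is 0.6 − 0.6 = 0, so the residual variance stays at 0.80.
- Change with Phase I change: Var(P − Y13) = 0.80 + 1 − 1.20 = 0.60 and the covariance is −0.40, so 0.60 − 0.16/0.80 = 0.40.
- Week 13 only: 0.80 − 0.36 = 0.44.
- Both scores: each coefficient is 0.6/1.6 = 0.375, so 0.80 − 2(0.6)(0.375) = 0.35.

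**Step 3: autoregressive, ρ = 0.6.**
- Cov(P, Y13) = (0.6 + 0.36)/2 = 0.48, and Cov(P, Y0) = (0.36 + 0.216)/2 = 0.288.
- Weeks 26/52 with Phase I change: 0.80 − 0.192²/0.80 = 0.754.
- Change with Phase I change: 0.84 − 0.208²/0.80 = 0.786.
- Both scores: 0.80 − 0.48² = 0.570; week 0 adds nothing here.

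**Step 4: main effect over three levels, ρ = 0.6.** Residual variance is 0.711 (equal) or 0.595 (autoregressive). Rescaled by 9/4 for the two-thirds effect, this is 1.60 or 1.34.

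| Reading of the stated model | Equal: stated vs both scores (ratio) | Autoregressive: stated vs both scores (ratio) | Ratio over ρ 0.3–0.8: equal; autoregressive |
|---|---|---|---|
| Outcomes weeks 26 and 52 | 0.80 vs 0.35 (2.29) | 0.754 vs 0.570 (1.32) | 1.27–4.76; 1.04–2.22 |
| Change, or condition by time | 0.40 vs 0.35 (1.14) | 0.786 vs 0.570 (1.38) | 1.37–1.06; 1.69–1.18 |
| Main effect over weeks 13, 26, 52 (rescaled) | 1.60 vs 0.35 (4.57) | 1.34 vs 0.570 (2.35) | about 2.2–10; 1.5–4.5 |

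Each ratio is also the ratio of sample sizes needed for equal power. In the change row the loss shrinks as ρ rises; in the other rows it grows.

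**Step 5: unequal spacing.** If correlation decays with time at 0.6 per 13 weeks, the first two rows become 0.647 vs 0.514 and 0.794 vs 0.514.

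**The case against.** The strongest reply is that the damage depends on a model the plan does not state, and that the context favours the mildest reading. Weight and activity are both analysed as changes with a Phase I change as covariate, and the accountability mediator is itself a change from week 13. Under that reading the week-13 score enters through the outcome, and under equal correlation of 0.6 the loss is only 0.40 against 0.35. The stated model then even does slightly better than week-13 adjustment alone (0.40 against 0.44). This stands, and it rules out several stronger statements that a reader might infer.

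- *That the comparison necessarily loses about half its precision.* The contrast of 0.80 with 0.35 needs weeks 26 and 52 as the outcomes and exactly equal correlation. The document establishes neither.
- *That the arm effect is diluted.* This follows only for a condition main effect that includes week 13 as a level.
- *That chance imbalance at week 13 stays in the estimate.* Not in general. Under the change reading with equal correlation of 0.6, the slope on Phase I change is −0.40/0.80 = −0.5, so the estimate is the arm difference in P minus 0.5 times the difference at week 13 minus 0.5 times that at week 0. Both earlier scores are adjusted for, with weights of 0.5 where 0.375 would be best.
- *That the comparison is biased.* Phase I change precedes the randomised treatment, so adjusting for it does not bias the arm contrast.

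It is also fair that this is a mechanism measure in a pilot with no power claim attached, that week-52 collection of the scale is inferred, and that a change of model after follow-up is post hoc. None of this removes the algebraic result: no reading examined makes the single difference score more precise than the two scores, beyond the one degree of freedom.

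**Conclusion.** The point holds as one of efficiency and clarity. The stated covariate is never better than the week-13 and week-0 scores entered separately. At ρ = 0.6 the stated analysis has residual variance about 1.1 to 1.4 times as large under the change or condition-by-time reading, and 1.3 to 2.3 times as large if weeks 26 and 52 are the outcomes. Only a main effect over weeks 13, 26 and 52 adds dilution to two thirds.

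The ordering follows from algebra. The sizes rest on assumed correlations, equal SDs, an equal effect at weeks 26 and 52, and the reading of Phase I change as the change in accountability itself. The finding bears on how the mechanism result is read; the weight, activity and retention comparisons do not depend on it. The change is worth making because the scores it needs are already implied by the plan's own analyses.

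**What to change.** Model only the post-randomisation accountability scores (week 26, and week 52 if the scale was given then) with arm, visit, arm by visit, and the week-13 and week-0 scores as two separate covariates in place of Phase I change. Report the arm difference with its confidence interval at each visit. Enter both scores: week 13 alone can be slightly less precise than the stated model under the change reading.

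State the weeks at which the scale was administered, and the repeated levels and tested term of the model as stated. Because follow-up ended in May 2019, present the new model as a labelled re-analysis beside the model as stated, without replacing it. The cost is one extra degree of freedom and a short re-run on existing data.
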